7.11.2 Laboratory Data

The clinical laboratory data will be summarized by scheduled time point, Part, and change from baseline. Any laboratory data below/above the limit of quantification will be summarized using the value of the limit of quantification (upper or lower, respectively). A listing will be provided where the values that are below the lower limit or above the upper limit of the reference range will be flagged. Those values or changes in values that are considered clinically significant by the investigator will also be flagged in the listing.

Repeated or unscheduled results will not be included in the by timepoint summaries but will be included when looking for extreme values and displayed in the individual data listings.

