#### 4.3 Study Drug Safety

The most common and anticipated adverse events related to pgsitacianine include infusion related reactions. These reactions occur in about 1 in 3 patients and tend to be mild or moderate in severity. In general, these reactions initiate within 5 minutes of infusion start and resolve within minutes after onset.

Over the doses evaluated in the Phase 1 ON-1001 study (0.1-1.2 mg/kg), pgsitacianine was well tolerated in patients with solid tumors (HNSCC, BC, CRC, or EC) and showed no dose-limiting toxicity (DLT) (hence the maximum tolerated dose was not reached during the study) or study-drug-related serious adverse events (SAEs). Since no pgsitacianine-related SAEs were reported in Phase 1a, the highest dose from Phase 1a [REDACTED] was selected for further evaluation of safety, PK, and imaging feasibility of pgsitacianine in Phase 1b in 15 additional patients across 4 tumor types (BC, HNSCC, CRC, EC) at administration [REDACTED] before surgery (and imaging).

In Phase 1a and 1b, all 30 patients (100%) experienced treatment-emergent adverse events (TEAEs). The most common TEAEs (ie, reported  $\geq 4$  patients overall) were procedural pain (21/30 patients, 70%), nausea (6/30 patients, 20%), wound complication (4/30 patients, 13%), and constipation (4/30 patients, 13%). The TEAEs of procedural pain and wound complication could be attributed to the surgical procedures (standard of care). Severe (Grade  $\geq 3$ ) TEAEs, none related to study drug, occurred in 6 (20%) patients. Overall, 3 patients experienced 4 TEAEs (dizziness, headache, pain in jaw, and flushing) considered possibly related to the study drug. All TEAEs considered related to study drug were mild (Grade 1) and experienced by patients in the [REDACTED] dose cohort. These TEAEs were consistent with typical complications known to occur following surgery, of which the Investigator could not completely rule out the possible contribution of pgsitacianine.

Transient increases in alanine aminotransferase (ALT) (up to 7 $\times$  upper limit of normal [ULN]), aspartate aminotransferase (AST) (up to 10 $\times$ ULN), and/or alkaline phosphatase (up to 3 $\times$ ULN) levels were reported in 4 patients at  $\geq 1$  time point after dosing; none of these abnormalities were considered to be related to the study drug; These elevations were judged by the Investigator to be complications due to the length of surgery and the duration of anesthesia.

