## 9.7 Safety Analysis

Safety data will be summarized by treatment group with descriptive statistics and frequency tables. In general, continuous data will be summarized by presenting the number of patients, mean, standard deviation, median, minimum, and maximum values. Categorical data will be summarized by presenting the number (frequency) and percentage of patients at each level of response. Subject disposition will be presented and summarized.

Adverse events will be coded using MedDRA, Version 24.0 or higher, by system organ class and preferred term, and a listing of all AEs will be generated. Treatment-emergent AEs (TEAEs), treatment-related TEAEs, TEAEs by intensity, TEAEs that lead to discontinuation of study drug, and SAEs will be summarized by treatment, system organ class, and preferred term.

The clinical laboratory data will be summarized by time point, treatment group, and change from baseline. The values that are below the lower limit or above the upper limit of the reference range will be flagged. Those values or changes in values that are considered clinically significant by the investigator will also be flagged. Repeated or unscheduled results will not be included in the summary statistics but will be included in the individual data listings.

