2. STUDY OBJECTIVES

2.1 Objectives and Endpoints

The primary objective of this study is to investigate whether pegasitacianine can detect clinically significant events (CSEs) at the patient level, which include:

1. The detection of disease that cannot be detected using standard procedures during the surgical resection of lung malignancies
2. The detection of synchronous lesions
3. The detection of positive surgical margins following primary tumor resection
4. Tumor-negative standard of care (SOC) biopsies

Table 1. Objectives and Endpoints

Objectives	Endpoints
Primary Objective	Primary Endpoint
The primary objective of this study is to investigate whether pegasitacianine can detect clinically significant events (CSEs) at the patient level.	Rate of CSEs, which include: 
1. The detection of disease that cannot be detected using standard procedures during the surgical resection of lung malignancies2. The detection of synchronous lesions3. The detection of positive surgical margins following primary tumor resection4. Tumor-negative standard of care (SOC) biopsies

Secondary Objectives	Secondary Endpoints
Determine sensitivity, specificity, negative predictive values (NPPV), and positive predictive values (PPV) of the imaging agent at the level of the individual specimens, including lymph nodes.	Sensitivity, specificity, negative predictive values (NPV), and positive predictive values (PPV) at the specimen-level.
Evaluate safety and toxicity of pegsitacianine.	Incidence of TEAEs and SAEs, abnormalities in lab values, vital signs, or ECG results.
Exploratory Objectives	Exploratory Endpoints
Assess the how the SBR affects the diagnostic accuracy of pegsitacianine in detection of metastatic disease vs. normal tissue.	ROC analysis across various tumor-to-background ratio fluorescence thresholds.
Effect of camera system on diagnostic results.	Diagnostic results across various camera systems.
Assess amount of fluorescence shown in various types of specimens.	Mean fluorescence intensity and Specimen-to-background ratio

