7.2 Reporting Conventions

The following conventions will be applied to all data presentations and analyses:

- Continuous variables will generally be summarized by the number of patients with missing and non-missing values, mean, standard deviation, median, Q1 (quartile 1), Q3 (quartile 3), minimum, and maximum.
- Categorical variables will be summarized by the number and percentage of patients within each category. If not specified otherwise, the number of patients with non-missing values will be the denominator for percentage calculations. The number of patients with missing values will be presented.
- Confidence intervals will be reported as two sided at the 95% level.
- All mean and median values will be formatted to one more decimal place than the measured value.
- Standard deviation values will be formatted to two more decimal places than the measured value.
- Minimum and maximum values will be presented with the same number of decimal places as the measured value.
- The number and percent of responses will be presented in the form XX (XX %), where the percentage is in parentheses. Percentages will be rounded to the nearest percent. In

the case of a frequency of zero, the frequency and percentage will be presented as 0 rather than 0 (0%).

- Date variables will be formatted as DDMMYY for presentation

All the analyses will be run displaying the results from Part 1. All rates will be summarized using counts and percentages.

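### SAP 7.11.2 transposes the lower and upper limits in its rule for summarizing laboratory results outside the quantification range

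*SAP*

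**What the plan says.** The rule is in SAP 7.11.2 (Laboratory Data): "Any laboratory data below/above the limit of quantification will be summarized using the value of the limit of quantification (upper or lower, respectively". It feeds the tables described just before it: "The clinical laboratory data will be summarized by scheduled time point, Part, and change from baseline". SAP 7.2 says that continuous variables are generally described by counts of missing and non-missing values and by "mean, standard deviation, median, Q1 (quartile 1), Q3 (quartile 3), minimum, and maximum".

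The sentence after the rule puts the limits in the natural order, but for a different purpose, flagging against the reference range: "A listing will be provided where the values that are below the lower limit or above the upper limit of the reference range will be" marked as such. It is followed by: "Those values or changes in values that are considered clinically significant by the investigator will also be flagged in the listing".

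Protocol 9.7 has no rule for results outside the quantification range. Its flagging sentence also uses the natural order: "The values that are below the lower limit or above the upper limit of the reference range will be flagged". SAP 1 gives the SAP precedence over the protocol on analyses and reporting, and SAP 8 plans no deviations. The sentence in 7.11.2 is therefore the only rule on this matter and the one that governs.

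**The concern.** The sentence names two cases in one order (below, then above) and two substitutes in the opposite order (upper, then lower), and ties them together with *respectively*. Taken at its word, it assigns each out-of-range result the limit at the far end of the scale.

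This matters because it is an operative derivation rule. Followed literally, it would turn a result too high to quantify into the lowest quantifiable value in the by-visit table, and a result too low to quantify into the highest. The change-from-baseline table would inherit the error. Table 1 in SAP 2.1 counts laboratory abnormalities within the secondary safety endpoint ("Incidence of TEAEs and SAEs, abnormalities in lab values, vital signs, or ECG results"), so the tables that support it should not rest on a reversed rule. The written plan is also what the programs and outputs are checked against: under SAP 7.1 the final review confirms consistency with the SAP.

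**Working it through.** There is no plan figure to reproduce. The check is a reading of the text, followed by an illustration.

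**Reading the sentence**

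| Result reported as | Limit assigned by the SAP 7.11.2 wording | Limit that must be meant |
|---|---|---|
| Below the range | Upper | Lower |
| Above the range | Lower | Upper |

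The reference-range sentences in SAP 7.11.2 and Protocol 9.7 pair below with lower and above with upper. They show the intent, but they concern reference ranges, so they do not amend the rule.

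**Illustration: result above the range**

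From the documents: 40 planned subjects (SAP 4). Assumed, because the documents give no assay limits: lower limit L = 5 U/L; upper limit U = 500, 1000 or 2000 U/L; all 40 patients at 25 U/L at baseline; after dosing, 39 at 25 U/L and one above U.

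With v the substituted value:
- mean = (39 × 25 + v)/40
- SD = |v − 25|/√40 (one value differs from 39 equal ones)
- that patient's change = v − 25

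| Rule | v | Mean | SD | Min | Max | Patient's change |
|---|---|---|---|---|---|---|
| As written | 5 | (975 + 5)/40 = 24.5 | 20/6.325 = 3.2 | 5 | 25 | −20 |
| Corrected, U = 500 | 500 | 1475/40 = 36.9 | 475/6.325 = 75.1 | 25 | 500 | +475 |
| Corrected, U = 1000 | 1000 | 1975/40 = 49.4 | 975/6.325 = 154.2 | 25 | 1000 | +975 |
| Corrected, U = 2000 | 2000 | 2975/40 = 74.4 | 1975/6.325 = 312.3 | 25 | 2000 | +1975 |

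The as-written row does not depend on U. The median and quartiles stay at 25 here. In real data, moving one value from one end of the ordering to the other can shift them slightly.

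**Illustration: result below the range**

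Assumed: limits 0.1 and 30; 39 values of 0.6 and one below 0.1.
- As written: mean (39 × 0.6 + 30)/40 = 53.4/40 = 1.335, maximum 30.
- Corrected: mean (39 × 0.6 + 0.1)/40 = 23.5/40 = 0.588, minimum 0.1, maximum 0.6.

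**When the sign of the change reverses**

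Suppose the baseline is within range and above L. A later result above the range is then a true rise, but it is recorded as L minus baseline, which is negative. If both results are above the range, the recorded change is 0 under either reading. If no result is out of range, the rule is never used and the effect is zero.

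**The case against.** The strongest reply is that this is a transposed word pair and not a method anyone chose. The neighbouring sentence shows what was meant. SAP 7.1 requires independent programming, output review and a senior statistical review, and literal implementation would mean programming a visibly absurd rule. Protocol 7.6 and 7.6.2 allow local laboratories and each institution's own panel, and neither document describes collecting quantification limits. If results arrive as a limit with a less-than or greater-than sign (an assumption about format), the limit in the record is already the right one. All of this stands, and it makes a real effect unlikely. It does not make the sentence correct: a programmer who follows the intent departs from the governing text.

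A reader might infer that the rule would conceal an extreme elevation from the trial report. The documents do not support that. The rule is worded for summaries only. The listing still flags results outside the reference range and those the investigator considers clinically significant. Protocol 8 has adverse events from laboratory findings recorded and CTCAE-graded, and SAP 7.11.1 tabulates treatment-emergent events by grade.

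A reader might also link the rule to Protocol 4.3, which reports from the Phase 1 study "Transient increases in alanine aminotransferase (ALT) (up to 7 $\times$ upper limit of normal" and AST up to 10 times that limit. These are given as numerical multiples, and nothing says that any exceeded a quantification limit; a quantified value is untouched by the rule. For scale, with an assumed upper limit of normal of 35 to 50 U/L, quantification limits of 500, 1000 and 2000 U/L lie at 10 to 14, 20 to 29 and 40 to 57 times that value, so none is below the largest multiple cited. The Phase 1 elevations are not evidence that the rule would be triggered.

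Finally, SAP 7.11.2 identifies abnormal values by flags in a listing, and no hypothesis test or decision rule uses laboratory means. The link to the secondary safety endpoint is therefore through descriptive tables only.

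**Conclusion.** The point holds as a wording error in an operative rule. As written, SAP 7.11.2 assigns the upper limit to results below the quantification range and the lower limit to results above it, and nothing in either document corrects it.

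Two conditions must both be met for any consequence: the rule is programmed literally, and at least one result falls outside the quantification range. The mean, SD, minimum, maximum and possibly the quartiles for that analyte and visit would then be wrong, and that patient's change from baseline could take the wrong sign. The size cannot be derived from the documents. The figures above rest on assumed limits and patient values, and the true effect may be zero. The primary endpoint and the diagnostic performance measures are not touched. This is a minor correction, worth making because it costs almost nothing.

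**What to change.** Replace the sentence in SAP 7.11.2 with: *Values reported below the lower limit of quantification will be summarized at the lower limit, and values reported above the upper limit of quantification at the upper limit.* It would help to add that listings show the result as the laboratory reported it, including any less-than or greater-than sign.

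The cost is one or two sentences, with no change to data, design or clinical procedures and no evident downside. SAP 7.1 allows the statistical methods to be updated before database lock. If the lock has passed, the clinical study report can state the pairing actually used, since the correction does not bear on the primary conclusions.

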7.11.3 Vital Signs

Vital signs data will be summarized by time point, Part, and change from baseline. A listing will also be provided.

Repeated or unscheduled results will not be included in the summary statistics but will be included in the individual data listings.

7.11.4 Physical Exam

Physical examination results will be provided as a listing.

7.11.5 ECG

ECG results will be provided as a listing.

8. DEVIATIONS FROM ANALYSIS AS DESCRIBED IN THE PROTOCOL

No deviations from the protocol are planned.

9. APPENDIX 1: SCHEDULE OF EVENTS

	Screening	Dosing		Treatment		
	Days -30 to -1	Day 0 Pre-Dose	Day 0 Post-Dose	Surgery █ - █	Day of Discharge	Day 21 (± 10 Days)
Evaluation						
Informed consent & subject enrollment	X					
Inclusion/exclusion criteria	X	X				
Pregnancy test ^a	X	X				X
Demographic data	X					
Medical history	X					
Physical examination	X				X	X
Karnofsky Performance Status	X					
Height ^b	X					
Body weight ^b	X	X				
Vital signs ^c	X	X	X ^d	X	X	X
12-lead electrocardiogram		X				X
Concomitant medications	X	X	X	X	X	X
Study drug administration			X ^e			
Adverse events review ^f			X	X	X	X

Serum chemistry	X	X		X	X	X
Hematology ^g	X	X		X	X	X
Surgery				X		
Intraoperative Imaging				X		
Pathology evaluation of surgical specimens				X ^h		

Footnotes

- ^a For female subjects, a serum sample or urine dipstick for a pregnancy test will be collected at screening and on Day 0 and Day 21.
- ^b Body mass index will be calculated at Screening only.
- ^c Vital sign measurements will include systolic and diastolic blood pressure, pulse, respiratory rate, and temperature (in degrees Celsius). Blood pressure and pulse will be measured after a resting period of at least 5 minutes in the supine position.
- ^d Patient's vital signs are to be recorded immediately after the infusion and 30 minutes afterward
- ^e The Sponsor recommends the use of prophylactic diphenhydramine prior to study drug administration, in an effort to reduce the prevalence of infusion-related reactions.
- ^f Patients will be assessed for AEs occurring from the time of dosing through Day 21 (± 10 days)
- ^g Hematology assessments may include hemoglobin, hematocrit, erythrocyte count (red blood cells), differential leukocytes, platelet count, and total leukocytes (white blood cells).
- ^h Pathologic analysis of surgical specimens will take place from the conclusion of surgery and up to 10 days after
